6.3 General calculation rules

Data will be listed with the observed number of decimal places. Summary statistics will be presented to the same number of decimal places as the observed data, apart from the means and medians (to one more decimal place), and standard deviations (two more decimal places). Calculated data and summary statistics of calculated data will be presented with an appropriate number of decimal places.

In case of replicate measurements (e. g. three determinations of a parameter at one planned timepoint), means of these measurements will be calculated and will be used for summary statistics without any prior rounding.

Form Valid From: 08/03/2024

Form Version: 1

101111 7 6131011

Record Title: Clinical Statistical Analysis Plan CT-P1-001

Record Title:

Data from unscheduled assessments will only be listed and not presented in summary statistics.

Relative study times and dates will be calculated with respect to the start time and date of the administration of study drug.

Calculation of relative days from onset of adverse events:

The relative day for onset of an adverse event is calculated as "day of onset" minus "day of start of treatment".

Duration of adverse events:

The duration of an adverse event (expressed in days) is calculated as "stop date" minus "start date" plus 1.

If parts of the start/stop date of an adverse event are missing (day, month, or year), the relative day for onset and/or the duration of the adverse event are not calculated.

In order to determine if an adverse event or the worsening of an adverse event is a treatmentemergent event, the following rules will be used as a worst-case scenario:

- If the date (and time) of onset or change is completely known, the adverse event is considered as treatment-emergent, provided the day (and time) of onset or change is after or on the same day (and time) as first study treatment.
- If the time of onset or change is missing, but the day, month and year is known, the adverse event is considered as treatment-emergent, provided the day of onset or change is after or on the same day as first study treatment, unless other information (e.g. stop date/time) suggest otherwise.

Calculation of absolute changes from baseline:

- post-dose value - baseline value

Calculation of relative changes from baseline:

- (post-dose value - baseline value)/baseline value

Frequencies / percentages for qualitative data:

- Number of observations (frequency)
- Percent

Percentages will be calculated as "frequencies" divided by the number of subjects in the population the analysis is based on (i.e. this may include missing data in the denominator).

Form Valid From: 08/03/2024

Form Version:

Record Title: Clinical Statistical Analysis Plan CT-P1-001

Record Title:

Descriptive statistics

Basic descriptive statistics for continuous data comprise:

- Number of observations (N)
- Arithmetic mean
- Standard deviation (SD)
- Minimum (Min)
- Lower quartile (Q1)
- Median
- Upper quartile (Q3)
- Maximum (Max)

Descriptive statistics for continuous variables assumed as log-normally distributed (e. g. PK parameters):

- Number of observations (N)
- Number of observations ≥ LLOQ (NLOQ)
- Arithmetic mean
- Arithmetic SD
- Arithmetic coefficient of variation (CV)
- Geometric mean
- Geometric SD
- Geometric CV (%) (gCV)
- Q1
- Median
- Q3
- Min
- Max

Analysis sets and data review criteria

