12.4 Follow-up of adverse events

All AEs will be followed until they have abated, or until a stable situation has been reached. Depending on the event, follow up may require additional tests or medical procedures as indicated, and/or referral to the general physician or a medical specialist. SAEs need to be reported till end of study within the Netherlands, as defined in the protocol.

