measurements, no data transformation of these measurements is required prior to statistical analysis. Minimum and maximum values for vital signs assessed within one day will be analyzed using descriptive summary statistics (including changes from baseline) by treatment group and time point (Day 1, Day 2, Day 3 etc.).

Data distribution for all vital signs (both averages of high-frequency data and single measurements) will be evaluated using the Kolmogorov-Smirnov test and, if applicable, normal/non-normal distribution will be reported. All variables will be expressed both as mean ± standard deviation (SD), as well as medians and interquartile ranges (IQR) in tables and graphical representations of the data. In case a value of one of these parameters is an outlier in a subject, this will be described separately.

Safety laboratory parameters & inflammatory parameters

All safety laboratory parameters (see the study protocol for a full overview) are measured at set intervals during the experimental protocol, as well as during each of the study's follow-up visits. All safety laboratory measurements represent single timepoint measurements, meaning no data transformation prior to analysis needs to be performed. Complete listings for laboratory values will be generated. Laboratory values outside the normal range will be marked. Minimum and maximum values will be reported (including changes from baseline) by treatment group and time point (Day 1, Day 2, Day 3 etc.). In case a value of one of these parameters is an outlier in a subject, this will be described separately.

Data distribution for all safety laboratory parameters will be evaluated using the Kolmogorov-Smirnov test and normal/non-normal distribution will be reported. All variables will be expressed both as mean ± standard deviation (SD), as well as medians and interquartile ranges (IQR) in tables and graphical representations of the data. In case a value of one of these parameters is an outlier in a subject, this will be described separately.

Results from laboratory tests will be summarized by treatment group and time point using descriptive summary statistics, including changes from baseline. Relative changes (for laboratory values) from baseline to follow-up visits (post-study drug administration minus baseline) will be categorized as:

Maximum increase from baseline: (maximum value post-study drug administration – baseline) / baseline

 \geq 1.5, \geq 2.0

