 Maximum decrease from baseline: (baseline - minimum value post-study drug administration) / baseline

≤ 0.5

Form Valid From: 08/03/2024

Form Version:

Record Title: Clinical Statistical Analysis Plan CT-P1-001

Record Title:

A frequency table by treatment dose will be generated for these categorized changes.

In addition, changes from "from within normal range to above normal range" will be evaluated and categorized as:

"changes to at least 1.5-time upper limit normal", "changes to at least twice upper limit normal".

A frequency table by treatment will be generated for these categorized changes from normal at baseline.

In case a value of one of these parameters is an outlier in a subject, this will be described separately.

12-lead ECG parameters

Non-quantifiable differences in ECG's deemed to be of clinical relevance by a clinical investigator will be registered as an (S)AE. For differences in ECG-related (S)AEs, the same ground-rules apply as those listed under reported number of adverse events and local tolerability (please refer to this section). Frequencies of overall interpretation (normal, abnormal and clinically not significant, abnormal and clinically significant) will be tabulated by treatment group and time point.

For numerically quantifiable differences in ECG-parameters (e.g. QTc-time, see the study protocol for a full overview), data distribution will be assessed using the Kolmogorov-Smirnov test and normal/non-normal distribution will be reported. Individual measurement timepoints will be expressed as both mean ± standard deviation (SD), as well as medians and interquartile ranges (IQR).

Extent of exposure

Total exposure [mg] and relative exposure [mg/kg] will be analyzed by descriptive summary statistics.

8.6 **Analysis of secondary endpoints**

Pharmacokinetic data analyses

The PK parameters will be analyzed by descriptive summary statistics. AK1967 concentration-time profiles for individual subjects will be analyzed with non-compartmental approaches using a validated commercially available software package (WinNonlin, version 8.4, Pharsight Corporation, Mountain View, CA). Nominal times will be used in the analysis. For data reported as BLQ and ALQ (below and above limit of quantification, respectively), the low and high limit of detection value will be used in the analysis.

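### SAP 6.3 restricts unscheduled assessments to listings, so read plainly the maximum-change and ULN-shift laboratory tables can miss a subject's worst post-dose value.

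*SAP*

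**What the plan says.** SAP 6.3 (General calculation rules) sets the rule for the whole analysis: "Data from unscheduled assessments will only be listed and not presented in summary statistics". Neither SAP 8.5 nor the table list in SAP section 9 makes an exception for safety. The same section averages replicate measurements at a planned time point before they are summarised.

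Protocol 12.4 expects tests outside the schedule: "Depending on the event, follow up may require additional tests or medical procedures as indicated".

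SAP 8.5 plans two kinds of laboratory output.

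- **By time point.** "Minimum and maximum values will be reported (including changes from baseline) by treatment group and time point". Vital-sign extremes and the counts of overall ECG interpretation are also reported by group and time point.
- **Per subject, over the post-dose period.** The maximum increase is built on the "maximum value post-study drug administration", with a matching minimum for the decrease, and is tabulated by category. The text introducing it reads "Relative changes (for laboratory values) from baseline to follow-up visits". A second table counts subjects who move from normal to at least 1.5 times the ULN, or show "changes to at least twice upper limit normal": "A frequency table by treatment will be generated for these categorized changes from normal at baseline".

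SAP 8.5 also provides: "Complete listings for laboratory values will be generated. Laboratory values outside the normal range will be marked".

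**The concern.** Keeping unscheduled values out of by-time-point means and medians is sensible. They come from selected subjects at irregular times and would distort an average.

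The maximum-change and ULN-shift tables do a different job. They count how many subjects ever reached a marked change. A value obtained because something needed following up is informative for that count, and leaving it out makes the omission depend on the outcome. Safety is the primary objective and its analysis is descriptive, so these counts are part of the primary result. With six subjects per dose group, one miscounted subject is visible in the percentage.

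**Working it through.** The plan gives no figure to reproduce, so the check sets the text side by side and then shows the size with an assumed example.

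**Step 1. Does the 6.3 rule reach these tables?** The rule has two halves: unscheduled data are listed only, and they are not in summary statistics. SAP 6.3 treats frequencies and descriptive statistics under separate headings, so one could argue that a frequency table is not a summary statistic. But a frequency table is not a listing either, so the first half still excludes it. The 8.5 formula has no scheduled-only limit, while its lead-in, which speaks of follow-up visits, leans towards scheduled values. The ULN table names no time point, so I read it as a per-subject worst value too. The plain reading is exclusion. At best, 6.3 and 8.5 are unreconciled and two programmers could produce different tables.

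**Step 2. When could a worst value be unscheduled?** Protocol Table 8 gives 13 post-dose biochemistry times: 0.5, 1, 2, 4, 6, 10, 24 and 48 hours, and days 3, 7, 14, 21 and 28. Nine fall by day 3. After that the gaps are 7 − 3 = 4 days, then 7, 7 and 7 days. A peak inside one of those gaps can be seen only at an unscheduled test.

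**Step 3. Effect on one subject.** Assumed values: baseline 25 and ULN 45, so 1.5 × ULN = 67.5 and 2 × ULN = 90. The relative increase is (maximum − baseline) / baseline, with categories at 1.5 and 2.0.

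| Case | Values used | Maximum | Relative increase | Multiple of ULN | Increase categories met |
|---|---|---|---|---|---|
| A, scheduled only | 26, 60, 40 | 60 | (60 − 25)/25 = 1.4 | 60/45 = 1.3 | none |
| A, with unscheduled 95 | 26, 60, 95, 40 | 95 | (95 − 25)/25 = 2.8 | 95/45 = 2.1 | all four |
| B, scheduled only | 26, 95, 40 | 95 | 2.8 | 2.1 | all four |
| B, with unscheduled 60 | 26, 95, 60, 40 | 95 | 2.8 | 2.1 | all four |

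In case A the subject is lost from every increase category. In case B the repeat is lower than the scheduled value that prompted it, and nothing is lost.

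**Step 4. Effect on the dose group.** SAP 3.1 gives 6 subjects per dose. One subject moves a cell from 0/6 = 0% (exact 95% interval 0 to 45.9%) to 1/6 = 16.7% (0.4 to 64.1%).

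**Step 5. Replicates.** No rule separates an unscheduled repeat from a replicate. If 95 and 60 in case B were averaged as replicates, the result would be (95 + 60)/2 = 77.5. That is a relative increase of (77.5 − 25)/25 = 2.1 and 77.5/45 = 1.7 times the ULN, so the subject would leave the 2 × ULN category.

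**The case against.** The strongest reply is that these subjects are not hidden. A test done under Protocol 12.4 follows an adverse event that should already be recorded, so the subject appears in the adverse event tables, one of which covers vital-sign and laboratory changes. Out-of-range values are marked in the listings, outliers are described separately, and 24 subjects can be read line by line. Dose escalation rests on the DSMB's interim safety reports, not on these end-of-study tables. All of this stands and limits the consequence. It does not repair the count: a listing gives no number by dose, the SAP does not define an outlier, and an adverse event table does not apply the ULN thresholds.

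A reader might infer more than the documents support:

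- **That unscheduled data are barred from every summary.** The rule does not stop the underlying event from reaching the adverse event tables, or the value from being described as an outlier.
- **That the laboratory and vital-sign minima and maxima and the ECG interpretation counts are defective too.** They are planned by time point, where excluding unscheduled values is appropriate. The SAP plans no overall QTc maximum that could be affected.
- **That every repeat of an abnormal result is lost.** The scheduled result that prompted the repeat stays in the tables, as case B shows.
- **That a peak between visits is likely.** Nothing in the documents says so. Protocol 3.1 describes a short half-life and, in animal disease models, therapeutic effects within 24 to 48 hours, a period with dense sampling.

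**Conclusion.** The point holds for two laboratory outputs: the categories of maximum increase and decrease from baseline, and the ULN-shift table. On the plain reading of SAP 6.3, an unscheduled value does not enter them. The loss is confined to a subject whose unscheduled value is more extreme than every scheduled post-dose value and crosses a category boundary that no scheduled value crosses. Each such subject costs 16.7 percentage points in a group of six.

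How often this would happen cannot be derived from the documents, and the values in the example are assumed. The conclusion also rests on the data review plan, cited in SAP 7.2 but not among the documents reviewed, not already settling the matter. Severity is minor to moderate: a correction worth making because it is nearly free, not a threat to the trial's conclusions.

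**What to change.** Amend SAP 6.3 and repeat the substance in SAP 8.5, along these lines:

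> Unscheduled assessments are listed and are excluded from by-time-point summaries, including by-time-point minima and maxima and ECG interpretation counts. The frequency tables of maximum increase and decrease from baseline, and of changes to at least 1.5 and 2 times the ULN, use all post-dose values, scheduled and unscheduled. Unscheduled repeats are not averaged as replicates.

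Align the 8.5 lead-in on follow-up visits with this text, and check it against the data review plan. The cost is a short text change and a programming flag on data that are listed anyway. No visit, sample or test is added. Make the change before database lock and unblinding.

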7.1 Data sets for analysis

A general definition of data sets for analysis will be:

Full analysis set

The full analysis set includes all randomized subjects who

- have received study medication
- have follow up data for the study primary and secondary outcomes

Form Valid From: 08/03/2024

Form Version: 1

Record Title: Clinical Statistical Analysis Plan CT-P1-001

For the analysis per dose, subject that did not receive the dose per protocol should be grouped to the dosing group closest to the administered dose or analysed and reported separately.

Record Title:

Pharmacokinetic analysis set (PKS)

The pharmacokinetic analysis set includes all subjects who:

- received the study medication
- showed sufficient compliance concerning medication, i.e. received the full dose of study medication
- have sufficient concentration PK data to calculate reliable estimates of at least one PK parameter
- are without any protocol violation that would interfere with the interpretation of the PK data.

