Fili	ng: h	ttps:/	/fourteenfour.dhcvisioncloud.com/dhcvision/document.jsp?key=DATABASE:1001;IO:1527897	Page 1 of 22	

Form printed on

Form FB_00079_Statistical Analysis Plan

Form Valid From: 08/03/2024

Form Version: 1

Record Title:

Record Title: Clinical Statistical Analysis Plan CT-P1-001

	8.6	Analysis of secondary endpoints	15
	Des	scriptive pharmacokinetic analyses	16
	8.7	Additional analyses	18
9	Cor	ntents of statistical tables and figures	19

Form Valid From: 08/03/2024

Form Version: 1

Record Title:

Record Title: Clinical Statistical Analysis Plan CT-P1-001

1 Background and scope

This SAP is created for the study and protocol as stated below:

Table 1 Basic trial information.

EU-CT number	2023-507035-37-00	
Trial name	Not applicable	
Clinical Trial Protocol Version	Latest Version 5	

All abbreviations are included in the Glossary

The following documents are attached to the QM record of this SAP:

- None (the Data Review Plan and Report are referenced in DHC VISION)

2 Study objectives

The objective of the AK1967 Phase 1 study is to evaluate the safety and tolerability of single escalating doses of AK1967 in healthy male volunteers. Main trial endpoints associated with this objective are fully described in the study protocol. To summarize, endpoints for this safety outcome are defined as differences between the different AK1967 dosage groups and the placebo group in:

- Reported number of adverse events after IMP administration
- Kinetics of vital signs at baseline and following IMP administration
- Local tolerability at site of IMP infusion
- Safety laboratory parameters at baseline and following IMP administration
- 12-lead electrocardiogram (ECG) parameters at baseline and following IMP administration

There are several secondary trial objectives. A full overview is again provided in the study protocol. To summarize, secondary trial measurements/endpoints discussed in this document include:

- Pharmacokinetics of the IMP (including AUC, C_{max} , Terminal $T_{1/2}$, clearance, VD)
- Pharmacodynamics (enzyme activity and concentration of DPP3) at baseline and following IMP administration.
- Pharmacodynamics related to the renin-angiotensin system (blood plasma levels of renin-angiotensin system metabolites) at baseline and following IMP administration
- Pharmacodynamics related to catecholamines (blood plasma levels of adrenergic metabolites) at baseline and following IMP administration

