7.2 Handling of missing data, drop-outs, extreme values and protocol violations

For an overview of checks for identification of protocol violations and data review, please refer to the data review plan.

8 Data analysis

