8.2 Definitions, derived variables and handling of missing data

Definitions of time points / time windows

Baseline will be defined per parameter and will be the value/measurement at the following timepoints:

Parameter for	Timepoint
Demographics	Screening
Vital signs	Baseline (before IMP administration)
ECG	Baseline (Screening)
Local laboratory assessment	Baseline (before IMP administration)
Arterial blood gas analysis	Baseline (before IMP administration)

Filing: https://fourteenfour.dhcvisioncloud.com/dhcvision/document.jsp?key=DATABASE:1001;IO:1527897	Page 11 of 22
---	---------------

Form Valid From: 08/03/2024

Form Version:

Record Title:

Record Title: Clinical Statistical Analysis Plan CT-P1-001

Parameter for	Timepoint
Biomarker (DPP3 concentration and	Baseline (before IMP administration)
activity)	

Derived variables

Extent of exposure:

Extent of exposure will be defined as total exposure in mg and calculated as:

total exposure
$$[mg] = 20 \frac{mg}{ml} * IMP volume [ml] * factor$$

where IMP volume is the body weight adjusted IMP volume before addition of NaCl and factor equals 1 for treatment group 12 mg/kg AK1967, 1/2 for treatment group 6 mg/kg AK1967, and 1/4 for treatment group 3 mg/kg AK1967. Total exposure will not be calculated for the Placebo treatment group.

In case of premature termination of the infusion, total exposure will additionally be multiplied by $\frac{volume\ administered\ [ml]}{c}$ in order to account for only partly administration of study drug.

Exposure per kg body weight will be calculated as:

Exposure per kg body weight
$$\left[\frac{mg}{kg}\right] = \frac{total\ exposure\ [mg]}{body\ weight\ [kg]}$$

Body mass index (BMI):

$$BMI = \frac{Weight [kg]}{Height [m]^2}$$

Handling of missing values

Data from subjects who prematurely terminate the trial will be used to the maximum possible extent. Missing values will not be inputted.

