8.3 Disposition

An overview of all subjects who entered the study, who were randomized and who completed the study will be provided by treatment group and overall.

Demographic data, screening and baseline characteristics

Demographic data and baseline characteristics will be summarized for the safety analysis set. Screening data (prior to study participation) will be shown as listings.

Filing: https://fourteenfour.dhcvisioncloud.com/dhcvision/document.jsp?key=	DATABASE:1001;IO:1527897	Page 12 of 22
---	--------------------------	---------------

Form Valid From: 08/03/2024

Form Version: 1

TOTTI VCISIOTI.

Record Title: Clinical Statistical Analysis Plan CT-P1-001

Record Title:

Demographic data and baseline characteristics

Summary statistics will be presented for age, weight, height, BMI, vital signs at screening and baseline (body temperature, heart rate, MAP, systolic and diastolic blood pressure, respiratory rate), Hb, Hct, leukocytes, leukocyte differential blood count, thrombocytes, sodium, potassium, creatinine, urea, alkaline phosphatase, ALT, AST, bilirubin, GGT, CK, CRP, PT, APTT, fibrinogen. Frequency tables for qualitative data (gender, age) will be provided. In case a value of one of these parameters is an outlier in a subject, this will be described separately.

In order to check for a potential disbalance of baseline characteristics of the three treatment groups, the Kruskal-Wallis test will be performed for continuous baseline characteristics.

Categorical variables will be compared using the Chi² test for contingency tables.

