8.5 Analysis of primary endpoints

The analyses of the endpoints for safety and tolerability will be performed on the full analysis set.

Reported number of Adverse Events and local tolerability

Adverse events (including assessment of local tolerability at the infusion site, which is reported in an AE format as well) will be recorded from the moment of study drug infusion, throughout the study and the follow-up visits. The same accounts for serious adverse events. (S)AEs will be categorized into different organ-systems based on reported symptoms. (S)AEs represent a categorical variable, meaning they are summarized as counts and percentages for different dosage groups. Consequently, no formal data distribution assessment can be performed for this datatype.

An overview of all adverse events (original term) will be generated as subject data listings, including onset relative to start of treatment, duration, intensity, seriousness and potential relationship to the study drug, action taken and outcome. The incidence of treatment-emergent adverse events as well as number of subjects with treatment-emergent adverse events will be summarized by potential relationship to the study drug (certain, probable/likely, possible, unlikely, unrelated) for all treatment groups.

Vital signs

All determined vital signs (oxygenation, heart rate, systolic, diastolic -and mean arterial blood pressure) are registered continuously during the experimental protocol at a measurement frequency once per 5 seconds. Artefacts may be removed. This high-frequency data will first be averaged into 10-minute intervals (calculating simple moving averages), as a correction measure for registration of spurious measurements. The exception for this approach is temperature, for which no high-frequency measurements are performed, meaning no data transformation is required prior to statistical analysis. As vital signs measured during each of the follow-up visits also represent single

Filing: https://fourteenfour.dhcvisioncloud.com/dhcvision/document.jsp?key=DATABASE:1001;IO:1527897

Page 13 of 22

Form Valid From: 08/03/2024

Form Version: 1

Record Title: Clinical Statistical Analysis Plan CT-P1-001

Record Title:

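### SAP 7.1 lets a reaction that stops the infusion decide which dose column counts it, and the safety set carries a follow-up-data condition that the protocol does not have

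*SAP*

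**What the plan says.** **Dose grouping.** Under the full analysis set, SAP 7.1 provides that, for the analysis per dose, a subject who "did not receive the dose per protocol should be grouped to the dosing group closest to the administered dose or analysed and reported separately". It gives no criterion for choosing between the two options and no exception for an infusion stopped because of an event.

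**Stopped infusions.** Protocol 3.2 and 7.1.3 both give the 2-hour infusion as a means of stopping if a reaction is seen. SAP 8.2 also foresees this: "In case of premature termination of the infusion, total exposure will additionally be multiplied by" a fraction based on the volume administered.

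**Analysis set.** SAP 8.5 states: "The analyses of the endpoints for safety and tolerability will be performed on the full analysis set". SAP 7.1 limits that set to randomised subjects who received study medication and who "have follow up data for the study primary and secondary outcomes". Protocol 13.2 asks only that study medication was successfully received, and Protocol 13.6.1 only that the subject was dosed. The demographic section after SAP 8.3 uses another name: "Demographic data and baseline characteristics will be summarized for the safety analysis set". SAP 7.1 does not define that set.

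**Related text.** On early terminators, SAP 8.2 says: "Data from subjects who prematurely terminate the trial will be used to the maximum possible extent". On protocol violations, SAP 7.2 says: "For an overview of checks for identification of protocol violations and data review, please refer to the data review plan". SAP section 1 notes that "the Data Review Plan and Report are referenced in DHC VISION".

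**The concern.** A subject whose infusion is stopped has not received the planned dose, so the plain wording of SAP 7.1 reaches him. The stop may itself be the consequence of the adverse event being tabulated. The column that counts the event would then depend on the event. An early reaction leaves the dose level being given, and under the closest-dose option it is credited to a lower dose.

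Safety by dose is the primary endpoint, summarised as counts and percentages with six active subjects per dose. Moving one subject visibly changes that table. The pharmacokinetic set already requires the full dose, so in practice the regrouping rule acts on the set that carries safety.

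The follow-up-data condition raises a second question. A subject who leaves early after a reaction is one whom a safety analysis most needs to keep, and the SAP does not say how much follow-up satisfies the condition.

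**Working it through.** **Plan's own figure.** 3 dose groups × (6 active + 2 placebo) = 24, that is 18 active and 6 placebo. This agrees with Protocol 5.2 and SAP Table 2. There is no power calculation to reproduce (SAP 3.1).

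**Inputs.** Doses 3, 6 and 12 mg/kg with n = 6 each, infused over 2 hours (SAP section 3). Adverse events are counts and percentages by dosage group (SAP 8.5), divided by the number of subjects in the analysis population (SAP 6.3). Subjects who stop after dosing are not replaced (Protocol 10.2).

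**Step 1: where the closest dose changes.** The boundary is the midpoint of adjacent doses.

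- (12 + 6)/2 = 9 mg/kg, which is 9/12 = 75% of the 12 mg/kg dose.
- (6 + 3)/2 = 4.5 mg/kg, which is 4.5/12 = 37.5% of 12 mg/kg and 4.5/6 = 75% of 6 mg/kg.
- If the pump rate is constant (an assumption), 0.75 × 120 = 90 min and 0.375 × 120 = 45 min.

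So a 12 mg/kg subject is closest to 6 mg/kg if he received 4.5 to 9 mg/kg, and to 3 mg/kg below that. A 3 mg/kg subject has no lower active group and leaves his column only by separate reporting.

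**Step 2: one reaction stops a 12 mg/kg infusion, with no other events.** Exact (Clopper-Pearson) 95% intervals are the 2.5% quantile of Beta(x, n−x+1) and the 97.5% quantile of Beta(x+1, n−x). For x = 0 the upper limit is 1 − 0.025^(1/n).

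| Situation | 12 mg/kg column | Where the event appears |
|---|---|---|
| Kept at assigned dose | 1/6 = 16.7% (0.4–64.1) | 12 mg/kg |
| Under 75% infused, closest dose | 0/5 = 0% (0–52.2) | lower dose: 0/6 (0–45.9) becomes 1/7 = 14.3% (0.4–57.9) |
| Under 75% infused, separate | 0/5 = 0% (0–52.2) | alone: 1/1 = 100% (2.5–100) |
| Over 75% infused, closest dose | 1/6 = 16.7% (0.4–64.1) | 12 mg/kg |
| Over 75% infused, separate | 0/5 = 0% (0–52.2) | alone: 1/1 = 100% (2.5–100) |

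Below 75%, both options empty the assigned column. Above 75%, the unstated choice decides.

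**Step 3: pooled active doses.** If he moves only between active doses, the pooled figure stays 1/18 = 5.6% (0.1–27.3).

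**Step 4: placebo.** SAP 6.1 lists placebo beside the doses. If it counted as a 0 mg/kg dosing group, a further midpoint would arise at (0 + 3)/2 = 1.5 mg/kg. SAP 3.1 and Table 2 use the term for the dose cohorts and call placebo the control group, so the table above leaves it out.

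**Step 5: the two definitions of who is analysed.** Protocol 13.2 and 13.6.1 require dosing. SAP 7.1, applied to safety through SAP 8.5, requires dosing plus follow-up data on the primary and secondary outcomes. The SAP does not say whether treatment-day data suffice or whether every outcome is needed. If a subject did fail the condition, 1/6 would become 0/5 and his event would appear in no dose column.

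**The case against.** The strongest reply is that stopping an infusion for a reaction is itself foreseen by the protocol, so such a subject may be regarded as dosed per protocol and the SAP 7.1 rule as meant for misdosing. SAP 8.2, the only SAP text that names stopped infusions, keeps the treatment-group factor and scales exposure by volume. That can be read as leaving the subject in his group. This reading is possible, but no words in SAP 7.1 impose it, and SAP 8.2 derives an exposure without assigning a table column.

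The data review plan might hold a grouping rule. SAP 7.2 cites it for checks that identify violations. It is not among the documents reviewed, so this stays open and the fix allows for it.

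Separate reporting is transparent, and grouping by received or assigned dose is an analysis choice. It is true that the subject stays visible. However, the assigned-dose percentage still omits his reaction, and a single rule based on dose received would leave the column dependent on the reaction.

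On the analysis set, the objection has force. Vital signs are recorded continuously for 24 hours (Protocol 10.3.2) and early terminators' data are to be used as far as possible, so treatment-day data may satisfy the condition. The protocol's requirement that medication was successfully received is also unclear for a partial infusion. Exclusion of an early leaver is possible but not shown.

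The by-subject listings keep the event, and the DSMB works from its own report per dose group (Protocol 10.3). Both points stand and limit the consequence.

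**Conclusion.** The concern holds as a matter of SAP wording. As written, SAP 7.1 covers partly infused subjects. Where less than 75% of a 12 or 6 mg/kg dose was infused, both options take an infusion-stopping reaction out of the assigned-dose column, changing 1/6 to 0/5. Above 75%, the table depends on a choice for which the SAP gives no criterion. The follow-up-data condition on the safety analysis departs from the protocol, and the safety analysis set is named but not defined.

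The percentages describe a hypothetical single reaction with no other events. The dose cut-points follow from the planned doses, with placebo not treated as a dosing group; only the minutes rest on a constant infusion rate. The intervals overlap widely, so the issue is correct descriptive reporting of the primary endpoint. No effect on a test, on the DSMB review, or on pooled active counts (for moves between active doses) is shown. It should be fixed, because the endpoint is primary and the remedy is small.

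**What to change.** Amend the SAP wording:

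- **Safety set.** Define in SAP 7.1 a safety analysis set of all randomised subjects in whom the infusion was started, with no follow-up-data condition. Use it in SAP 8.5 and for the demographic tables.
- **Partial infusions.** Summarise safety of partly infused subjects under the assigned dose level, with the mg/kg received shown alongside.
- **Regrouping.** Limit regrouping by dose received to preparation or dispensing errors, decided and documented before unblinding.
- **Data review plan.** If it already contains a grouping rule, cite it in SAP 7.1 and align it with the two points above.

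The cost is text only. No new data or subjects are needed, and exposure per kg is already derived in SAP 8.2.
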